1.1 Comprehensive Cumulative History

Protocol Version 3 dated 16Nov2016 supersedes Version 2 dated 12Oct2016. Below is a summary of changes:

- Section 9.2: Usage information was clarified to indicate that a subject may be treated bilaterally if a subject qualifies in both eyes, at the discretion of the Investigator.
- Sections 1.0 and 9.3.2: Anti-VEGF washout periods were updated to:
 - Lucentis (ranibizumab): 30-day washout
 - Avastin (bevacizumab): 30-day washout
 - Eylea (afibbercept): 60-day washout
 - Macugen (pegaptanib): 45-day washout
- Section 1.0: Updated exclusion criterion #5 from:

Previous PRP in the study eye or the need for PRP within 2 months from the time of study enrollment, based on the Investigator's opinion;
to
Previous PRP in the study eye within 4 months of study enrollment, or the need for PRP during the study based on the Investigator's opinion.
- Section 15.6: FA information was updated to clarify that fluorescein sodium dye is injected into the peripheral vein of the arm of the subject.

Protocol Version 2 dated 12Oct2016 supersedes Version 1 dated 09Jun2016. Below is a summary of the changes:

- General: Minor editorial and formatting changes occurred throughout the document for consistency and clarity purposes.
- Section 1.0: BCVA inclusion criterion was changed from:

BCVA of 0.3 to 1.2 ETDRS (logarithmic minimum angle of resolution; logMAR) in the study eye (85 to 40 letters equivalent),
to:
BCVA between 78 and 25 letters, inclusive, in the study eye at the screening/randomization visit using ETDRS testing (see Inclusion #3).
- Section 1.0: The following exclusion criterion was added: Uncontrolled glaucoma or ocular hypertension in the study eye defined as an IOP >25 millimeter of mercury (mmHg) regardless of concomitant treatment with IOP-lowering medications (see Exclusion #2).
- Section 1.0: Exclusion criterion for Triessence (triamcinolone acetonide) within 90 days of study enrollment was removed, as this treatment is already excluded under the criterion covering intravitreal/periocular steroids in the study eye (see Exclusion #7).
- Section 1.0: Retisert, another fluocinolone acetonide intravitreal implant, was added as another exclusion since it is similar to Illuvien (see Exclusion #8).
- Section 1.0: Exclusions related to pregnant or nursing females were combined into one criterion and acceptable contraception language was added (see Exclusion #22).
- Section 1.0: The concurrent enrollment in another clinical study exclusion was further defined to include studies evaluating investigational devices or drugs (see Exclusion #23).
- Sections 1.0, 8.0, 10.7, and 15.0: BCVA scores were revised to include required

letters by ETDRS testing rather than logMAR equivalents.

- Section 2.0: Overview of Study Plan was updated to clarify that the Visit 5 procedures should be completed in the event of early termination visits. A footnote was also added to clarify that all ocular assessments are to be completed for both eyes.
- Section 9.3: Permitted treatments were updated to clarify that Anti-VEGF treatments are allowed in the non-study eye during study participation. Prohibited treatments were updated to include Retisert (fluocinolone acetonide intravitreal implant).
- Section 10.5: It was clarified that the Visit 5 procedures should be completed in the event of early termination.
- Section 15.0: The BCVA with ETDRS testing procedure was updated to note that standardized ETDRS procedures should be utilized and the scores should be reported in letters.

2.0 OVERVIEW OF STUDY PLAN

Visit Number	1	2	3	4	5	Unscheduled
Visit Window	0 days	14 ± 2 days (2 weeks)	28 ± 2 days (4 weeks)	42 ± 2 days (6 weeks)	56 ± 2 days (8 weeks) or Early Termination	N/A
Procedure/Assessment						
Informed Consent	X					
Demographics	X					
Medical/Ocular History	X					
Concomitant Medications	X	X	X	X	X	X
Urine Pregnancy Test (UPT) ¹	X				X	(x)
HbA1c Test	X					
BCVA (ETDRS) ²	X	X	X	X	X	(x)
Slit Lamp Biomicroscopy ²	X	X	X	X	X	(x)
IOP by Tonopen or Applanation ²	X	X	X	X	X	(x)
Spectral Domain OCT ²	X	X	X	X	X	(x)
Indirect Ophthalmoscopy/Dilated Fundus Examination ²	X	X	X	X	X	(x)
Fundus Photography ²	X	X	X	X	X	(x)
Fluorescein Angiography ²	X		X			(x)
Inclusion/Exclusion	X					
Adverse events	X ³	X	X	X	X	X
Dispense IP	X	X				(x)
Dispense instructions/diary	X	X				(x)
Collect IP and dosing diary		X	X			(x)
(x) = as needed ¹ = Required for females of childbearing potential (i.e., who are not postmenopausal for at least 1 year or surgically sterile for at least 6 weeks from Visit 1 – Screening/Randomization) ² = Performed on both eyes ³ = collected from the time of informed consent						

3.0 ABBREVIATIONS

Abbreviation	Definition
AE	Adverse Event
AR	Adverse Reaction
BCVA	Best corrected visual acuity
BID	Twice daily
CFR	Code of Federal Regulations
CRA	Clinical Research Associate
CRO	Contract Research Organization
D	Diopters
DME	Diabetic Macular Edema
eCRF	Electronic Case Report Form
EDC	Electronic Data Capture
ETDRS	Early Treatment Diabetic Retinopathy Study
FA	Fluorescein angiography
FDA	Food and Drug Administration
GCP	Good Clinical Practice
HbA1c	Glycated hemoglobin
HIPAA	Health Insurance Portability and Accountability Act
HCL	Hydrochloric Acid
HPBCD	Hydroxypropyl-beta-cyclodextrin
IB	Investigator Brochure
ICH	International Conference on Harmonization
IEC	Independent Ethics Committee
IND	Investigational New Drug
IOP	Intraocular pressure
IP	Investigational Product
IRB	Institutional Review Board
ITT	Intent-to-treat
IWRS	Interactive Web Response System
logMAR	Logarithmic minimum angle of resolution
m	Meters
mg	Milligrams
mL	Milliliters
mm	Millimeter
mmHg	Millimeter of mercury
NaEDTA	Disodium ethylene diamine tetra acetate
NVD	Neovascularization of the optic disc
NVE	Neovascularization elsewhere
OCT	Optical coherence tomography
OD	Right eye
OS	Left eye
PDR	Proliferative Diabetic Retinopathy
pH	Power of hydrogen

Abbreviation	Definition
PI	Principal Investigator
PP	Per Protocol
PRP	Panretinal photocoagulation
SAE	Serious Adverse Event
SAR	Suspected Adverse Reaction
UPT	Urine Pregnancy Test
US	United States
VA	Visual acuity
VEGF	Vascular endothelial growth factor
YAG	Yttrium aluminium garnet
µm	Microns

5.0 INTRODUCTION

Diabetic macular edema is the result of breakdown of the blood-retinal barrier and/or insufficient activity of the retinal pigment epithelium to pump out fluid from the retina, and is a sight-threatening condition common in diabetic retinopathy. There is extensive evidence that angiogenic cytokines (e.g., VEGF) and inflammatory cytokines are involved in the development of DME. It is widely thought that these cytokines are responsible for the accumulation of fluid within and below the retina (Feng 2013, Funatsu 2009, Funk 2009, Kaneda 2011, Noma 2006, and Noma 2011).

Currently available treatments for DME include macular grid laser photocoagulation, anti-VEGF agents, and corticosteroids; though, none of these treatments is fully satisfactory (Ozkaya 2013). Laser photocoagulation is generally palliative, and may take many months to develop a therapeutic effect. Anti-VEGF therapies can require monthly intravitreal injections, and some patients do not respond to these treatments. Intravitreal corticosteroid therapy can cause cataract and increased IOP with long-term treatment, and also is not effective in all patients (Sarao 2014 and Shamsi 2013).

SF0166 is intended to address the current limitations in the treatment of DME, which requires intravitreal injection every 4 to 12 weeks under topical anesthesia. The frequent visits to a retina specialist required for intravitreal injection represent a significant burden to patients, particularly for DME patients, many of whom are of working age. An alternative mode of drug administration, particularly topical eye drops, represents a very attractive treatment option.

The objective of this study is to determine an efficacy and safety profile of SF0166 in humans. Preclinical studies with SF0166 have demonstrated notable anti-angiogenic activity, and shown that the fluorination in the compound does have a positive impact on the ability for the treatment to get to the back of the eye. Activity of SF0166 in VEGF-driven models appears similar to anti-VEGF biologics. Moreover, SF0166 also blocks angiogenic signaling driven by other growth factors (platelet-derived and fibroblast growth factor), so clinical efficacy could exceed that of marketed drugs that only target VEGF.

Based on the pre-clinical information, it is expected that the benefits of SF0166 outweigh the risks of its use.

6.0 ETHICS

This clinical study will be conducted in accordance with the principles of the Declaration of Helsinki, in compliance with the International Conference on Harmonization (ICH) E6 GCP Consolidated Guideline, and other applicable regulations. The Investigator and personnel will conduct the clinical study in compliance with the protocol. The Investigator will ensure that all personnel involved in the conduct of the study are qualified to perform their assigned responsibilities through relevant education, training, and experience.

Prior to study initiation, this protocol, the informed consent form, and any other written information given to subjects must be approved by an Independent Ethics Committee/Institutional Review Board (IEC/IRB). The Investigator must provide documentation of the IEC/IRB approval to the Sponsor. The approval must be dated and must identify the applicable protocol, amendments (if any), informed consent form, applicable recruiting materials, written information for the subject, and subject compensation. The IEC/IRB must be provided with a copy of the Investigator's Brochure (IB), any periodic safety updates, and all other information as required by local regulation and/or the IEC/IRB. At the end of the study, the Investigator will notify the IEC/IRB about the study's completion. The IEC/IRB must also be notified if the study is terminated prematurely. Finally, the Investigator will report to the IEC/IRB on the progress of the study at intervals stipulated by the IEC/IRB.

Voluntary informed consent will be obtained from every subject (and/or legal representative, as applicable) prior to the initiation of any screening or other study-related procedures. The Investigator should have a defined process for obtaining consent. Specifically, the Investigator, or designee, will explain the clinical study to each potential subject and the subject must indicate voluntary consent by signing and dating the approved informed consent form. The subject must be provided an opportunity to ask questions of the Investigator, and if required by local regulation, other qualified personnel. The Investigator must provide the subject with a copy of the consent form written in a language the subject understands.

The consent document must meet all applicable local laws and will provide subjects with information regarding the purpose, procedures, requirements, and restrictions of the study, along with any known risks and potential benefits associated with the IP, the available compensation, and the established provisions for maintaining confidentiality of personal protected health information. Subjects will be told about the voluntary nature of participation in the study. Subjects will be provided with contact information for the appropriate individuals should questions or concerns arise during the study. The subject also will be told that their records may be accessed by appropriate authorities and Sponsor-designated personnel. The Investigator must keep the original, signed copy of the consent and must provide a duplicate copy to each subject.

7.0 PROTOCOL AMENDMENTS

Modification of the protocol is prohibited without prior written agreement in the form of a protocol amendment. All amendments will be created by the Sponsor and must be approved by the IEC/IRB prior to implementation; except when required to mitigate immediate safety risks or when the changes involve only logistical or administrative revisions. Amendments may necessitate that the informed consent and other study-related material be revised. If the consent form is revised, all subjects currently enrolled in the study may be required by the IRB/IEC to sign the approved, revised informed consent form.

This is Version 3 (Amendment 2) of this protocol.

8.0 SUBJECT POPULATION

The study population includes approximately 40 subjects, 18 years of age or older, randomized at approximately 10 sites. The goal is to enroll 40 subjects, 20 in each study arm, allowing for a minimum of 30 subjects to complete the study. To participate in the study, the subject must have center-involved diabetic macular edema (i.e., retinal thickening secondary to type 1 or type 2 diabetes mellitus with DME and central subfield thickness ≥ 325 μm on spectral domain OCT) in the study eye, either be treatment naïve or have been previously treated in the study eye with an adequate washout period (see [Sections 1.0](#) and [9.3](#)), achieve BCVA between 78 and 25 letters, inclusive, in the study eye using ETDRS testing, with BCVA decrement primarily attributable to DME, be willing able to attend all study visits and adhere to study regimen, and be willing to give written informed consent.

The duration of study participation is 8 weeks (± 2 days); including an on-treatment period of 28 days, and a post-treatment follow-up period of 28 days.

The complete inclusion and exclusion criteria are presented in [Section 1.0](#).

9.0 TREATMENTS ADMINISTERED

Upon signing the informed consent form, the subject will be screened for eligibility. Once it is determined that all eligibility criteria have been met, subjects will be randomized to 1 of the 2 treatment arms according to the Interactive Web Response System (IWRS) system.

9.1 Identity of Investigational Products (IP)

The formulation of SF0166 Ophthalmic Solution consists of SF0166, hydroxypropyl-beta-cyclodextrin (HPBCD) (50 milligrams [mg]/milliliter [mL]), boric acid (10 mg/mL), disodium ethylene diamine tetra acetate (NaEDTA) (0.1%), benzalkonium chloride (0.02%) in water at power of hydrogen (pH) of 8. Two doses will be used in this study; a low dose (SF0166 2.5%) administered BID and a high dose (SF0166 5.0%) administered BID. The chemical composition of the IP is presented in [Table 9-1](#).

TABLE 9-1: SF0166 COMPOSITION

Ingredient	Function	Concentration (w/v)
SF0166	Active pharmaceutical ingredient	5.0% (high dose) or 2.5% (low dose)
Hydroxypropyl β- Cyclodextrin	Permeation enhancer and precipitation prevention	5.0%
Boric Acid	Buffering agent	1%
Na-EDTA	Metal chelator	0.1%
1N Hydrochloric Acid (HCl)	pH adjustment	As needed
Benzalkonium chloride	Preservative	0.02%
Sterile Water for Injection	Diluent	88.88% (high dose) or 91.38% (low dose)

9.1.1 Test Product 1

SF0166 2.5% (low dose) BID

9.1.2 Test Product 2

SF0166 5.0% (high dose) BID

9.1.3 Packaging

SF0166 will be packaged in multi-use, pre-sterilized, low-density polyethylene dropper bottles with a tamper-evident cap.

Both doses of the test product will be provided with investigational labels; including kit number, site number, subject number, instructions for use, and investigational use statement. The randomization kit boxes will include 2 cartons with the kit number, each containing 3 bottles of SF0166 and bearing the same kit number.

9.2 Usage

If a subject meets inclusion/exclusion criteria at Visit 1, the site will enter the required data into the IWRS in order to randomize the subject to a treatment arm. After subjects are randomized, they are dispensed SF0166 in 1 of 2 dose groups. The subject will use SF0166 BID for 28 days (1 drop in the study eye). If a subject qualifies in both eyes, SF0166 may be administered to both eyes (study eye and non-study eye) at the discretion of the Investigator. The study eye is defined as the eye with the worse BCVA at baseline (Visit 1 - Screening/Randomization).

At Visit 1, the site staff will dispense 1 carton (3 bottles) from the subject kit. At Visit 2, the site staff will collect the used IP bottles, and dispense an additional carton (3 bottles) from the kit. It is expected that subjects will use 2 bottles between each visit. The additional 3rd bottle in each carton is a back-up supply. If a subject requires a re-supply for any reason, an unscheduled re-supply can be completed through the IWRS.

SF0166 should be stored at 2–8°C and protected from light.

Throughout the study, the Investigator or designee will be responsible for the accounting of all IP. The Investigator must ensure that the IP are not used in an unauthorized manner.

9.3 Concomitant Treatments

9.3.1 Permitted Treatments

Medications not specifically excluded in [Section 9.3.2](#) may be taken as necessary. For clarity, the following are permitted:

- Anti-VEGF injections for treatment of the non-study eye, including:
 - Eylea (aflibercept)
 - Lucentis (ranibizumab)
 - Avastin (bevacizumab)
 - Macugen (pegaptanib)
- Concomitant treatment with antibiotics at the discretion of the Investigator
- Artificial tears

9.3.2 Prohibited Treatments

Use of the following treatments is not allowed during the study and for the timeframes specified:

- Within 36 months (3 years) prior to study enrollment
 - Illuvien (fluocinolone acetonide intravitreal implant)
 - Retisert (fluocinolone acetonide intravitreal implant)
- Within 180 days (6 months) prior to study enrollment
 - Ozurdex (dexamethasone intravitreal implant)
- Within 90 days (3 months) prior to study enrollment
 - Focal laser photocoagulation or intravitreal/periocular/topical ocular steroids of any type in the study eye
 - Any intraocular surgery in the study eye
 - Any change in dose to a concomitant topical ophthalmic medication in the study eye
- Within 60 days (2 months) prior to study enrollment
 - Eylea (aflibercept) in the study eye
- Within 45 days prior to enrollment
 - Macugen (pegaptanib) in the study eye
- Within 30 days (1 month) prior to enrollment

- Lucentis (ranibizumab) in the study eye
- Avastin (bevacizumab) in the study eye
- YAG laser treatment in study eye

Subjects taking a stable dose of topical ophthalmic medications at study enrollment should be instructed not to dose study medication within 1 hour of investigational product dosing.

9.4 Accountability

Upon receipt of the IP, site personnel designated to handle the IP will conduct an inventory of the shipment(s). The site personnel designated to handle the IP must maintain sufficient accountability records for the duration of the study. Study treatment dispensation and collection for each subject should be included in the IP accountability records. The records must be made available to the Clinical Research Associate (CRA) for the purposes of verifying and accounting the clinical IP. Any discrepancies between the observed disposition and the written account must be recorded along with an explanation. The Investigator is ultimately responsible, although he/she may delegate this responsibility, to return all used/unused IP at the conclusion of the study.

9.5 Compliance

Compliance will be assessed by comparing study drug accountability records with the dosing information recorded daily by the subject. The site will document this comparison along with verification of the numbers of used and unused study product bottles. The numbers of missed doses as assessed at each clinic visit should be documented in the electronic Case Report Form (eCRF).

9.6 Investigational Product (IP) Shipment and Assignment

The site will confirm all IP shipments received from the sponsor within the IWRS. Details of this process are outlined in a separate manual. Upon confirmation, the shipment will show as part of the site's IP stock.

9.7 Subject Confidentiality and Methods Used to Minimize Bias

The Investigator must ensure that the subject's anonymity is maintained throughout the course of the study. In particular, the Investigator must keep an enrollment log with confidential identifying information that corresponds to the subject numbers and initials of each study participant. At the end of the study, the Sponsor will collect a copy of the enrollment log without any identifying subject information. All documents submitted to the Sponsor will identify the subjects exclusively by number and demographic information. No other personally identifying information should be transmitted to the Sponsor, including subject initials.

The intent of masking is to limit the occurrence of conscious and unconscious bias in the conduct and interpretation of the clinical study. Bias could arise from the influence that the knowledge of a specific treatment assignment may have on the recruitment of subjects, their subsequent care, the assessment of endpoints, the handling of

withdrawals, etc. Therefore, the essential aim of masking is to prevent identification of the treatments by the Investigator, subject, and others associated with the conduct of the study.

Subjects will be assigned to a study arm according to the next available randomization schedule as assigned by the IWRS. The randomization schedule will be blocked to ensure a balance of study arms at the study level. The randomization scheme will be generated and maintained by the Sponsor. Individual subject randomization schemes will be unmasked after all study data has been verified, validated, and the database is locked.

Using a masked study team is a required activity designed to protect the masking of the study personnel at the site and at the Sponsor. The Sponsor involved in reporting, obtaining, and/or reviewing the clinical data will not be aware of the specific dose being administered.

For purposes of this study, the subject, Principal Investigator (PI), and site staff will be masked to the IP dose. Investigators, site staff members, and sponsor personnel directly involved with the study will not be aware of the randomized dose group for each randomized subject. In the event of a medical emergency where the knowledge of dose group is required, the Investigator will have the ability to learn the dose group in order to properly treat the medical emergency, but should only exercise this ability when absolutely necessary.

The masked site personnel must coordinate all study activities as necessary to protect masking and minimize bias during the study. This level of masking will be maintained throughout the conduct of the study.

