1.0 SYNOPSIS

Sponsor:	SciFluor Life Sciences, LLC [name] [name]
Protocol Number:	SF0166-C-001
Protocol Title:	A Phase I/II Randomized, Double-Masked, Multicenter Clinical Trial Designed to Evaluate the Safety and Exploratory Efficacy of SF0166 Topical Ophthalmic Solution in the Treatment of Diabetic Macular Edema
Investigational Product:	SF0166 Topical Ophthalmic Solution (SF0166)
Active Ingredient:	SF0166 ($\alpha_1\beta_3$ antagonists)
Number of Investigative Sites:	Approximately 10
Investigative Site Locations:	US
Number of Subjects:	Approximately 40 (20 in each arm)
Duration of Treatment:	28 days
Study Population:	Male and female subjects, aged 18 or older, with diabetic macular edema (i.e., retinal thickening secondary to type 1 or type 2 diabetes mellitus with DME with central subfield thickness ≥ 325 microns (μm) on spectral domain optical coherence tomography [OCT]) and no treatment with anti-vascular endothelial growth factor (VEGF) therapy within up to 60 days of study entry in the study eye
Objective(s):	To evaluate the safety and exploratory efficacy of SF0166 topical ophthalmic solution in patients with DME
Study Design & Methodology:	
This is a prospective, randomized, double-masked multicenter, Phase I/II clinical study in which approximately 40 eligible subjects with active DME will be randomized to 1 of 2 treatment arms in a 1:1 ratio as follows:
 
• SF0166 2.5% low dose twice daily (BID)• SF0166 5.0% high dose BID 
Randomization will be stratified by best-corrected visual acuity (BCVA) using Early Treatment Diabetic Retinopathy Study (ETDRS) testing (<40 letters versus ≥ 40 letters at Visit 1 – Screening/Randomization).
 
Eligibility and all site-related treatment decisions will be made based on Investigator assessment of OCT. All OCT images will also be reviewed by a central reading facility; however, eligibility is based on the Investigator's assessment at the time the

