	
potential study subject is examined. The primary efficacy outcome is determined by the OCT assessments from the reading center.
 
Study subjects will administer the randomly assigned treatment for 28 days. There is an additional 28-day post-treatment follow-up period. All study subjects will return for examination every 2 weeks for 8 weeks (2 months).
 
Clinical assessments will include slit-lamp examination, intraocular pressure (IOP) measurement, BCVA, OCT, fluorescein angiography (FA), and fundus photography. Adverse events (AEs) will be recorded at all study visits.
 
Rescue therapy with a VEGF inhibitor can be administered to any study subject who experiences a significant decrease in BCVA, defined as BCVA loss of >7 letters from baseline (Visit 1 – Screening/Randomization), accompanied by an increase in OCT central subfield thickness of >75μm as compared to the previous study visit, as assessed by the Investigator.
 
Potential study participants will be asked to sign an informed consent document prior to screening. Once it is determined that all eligibility criteria have been met, subjects will be randomized to 1 of the 2 treatment arms. All study subjects and site staff will be masked to the treatment assignment.
 
The safety and exploratory efficacy of SF0166 will be evaluated over the course of the study. Since this is Phase I/II clinical study, no formal hypotheses testing is planned; descriptive statistics will be used to summarize the study outcomes.

Treatments:	
• SF0166 2.5% low dose BID• SF0166 5.0% high dose BID
Subject Selection:	
Inclusion Criteria:
 
1. Male or female, 18 years of age or older.2. Retinal thickening secondary to type 1 or type 2 diabetes mellitus with DME defined as central subfield thickness \geq325 μm on spectral domain OCT in the study eye.3. BCVA between 78 and 25 letters, inclusive, in the study eye at the screening/randomization visit using ETDRS testing, with BCVA decrement primarily attributable to DME.4. Treatment naïve (i.e., no previous anti-VEGF treatment in the study eye) or previously treated study eye with adequate washout defined below:
a. Lucentis (ranibizumab): 30-day washout

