10.0 STUDY PROCEDURES

10.1 Visit 1 – Screening/Randomization

After obtaining written informed consent and Health Insurance Portability and Accountability Act (HIPAA) authorization, site staff will perform/assess the following in the order suggested below.

1. Each screened subject should be assigned a subject identifying number, based on the next available number in the eCRF.
2. Collect subject demographic information.
3. Collect ocular and non-ocular medical history.
4. Collect concomitant medications taken during the previous 12 months. Ask specifically about the use of Iluvien during the previous 36 months.
5. Administer UPT for female subjects of child-bearing potential.
6. Conduct in-office HbA1c test following test manufacturer guidelines.
7. Conduct the following ocular assessments on both eyes (refer to [Section 15.0](#) for further details):

- a. BCVA by ETDRS
- b. Slit-lamp Biomicroscopy
- c. IOP by Tonopen or Applanation
- d. Spectral Domain OCT
- e. Indirect Ophthalmoscopy/Dilated Fundus Examination
- f. Fundus Photography
- g. Fluorescein Angiography
8. Assess inclusion/exclusion criteria.
9. If subject is eligible, randomize the subject by entering information into the IWRS.
10. Dispense kit number provided by IWRS and provide dosing instructions/diary to the subject.
11. The first dose of study medication should be administered within the clinic under site staff supervision, and subsequent doses will be self-administered following the subject's visit.
12. Assess for any AEs occurring from the time of informed consent.
13. Provide instruction for the subject to:
 - a. Dose IP as instructed
 - b. Complete dosing information in subject diary.
 - c. Return for Visit 2 (Day 14) in 2 weeks (\pm 2 days).
14. Prepare and upload OCT images to the central reading center, and upload fundus photography to ShareFile.

Note: Subjects can be re-screened at the discretion of the Investigator if there is reasonable clinical evidence to suggest the subject may qualify after initial screen failure. The Investigator should contact the Sponsor to discuss re-screenings prior to conducting the visits.

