11.3.2.2 Analysis Methods

Descriptive statistics will be used to summarize the study outcomes. Continuous variables will be summarized by descriptive statistics (sample size, mean and standard deviation, median, minimum and maximum). Discrete variables will be summarized by frequencies and percentages. Any statistical tests performed to explore the data will be used only to highlight any interesting comparisons that may warrant further consideration.

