15.0 APPENDICES

15.1 BCVA (ETDRS)

The site staff should follow their standard procedures for conducting BCVA using ETDRS testing. The general procedure is as follows:

Overview

1. BCVA at a single site should be done consistently throughout the study using the same equipment, lighting conditions etc.
2. BCVA should be performed prior to instillation of any drops to dilate or anesthetize the eye and prior to any examination that requires contact with the eye, including the measurement of IOP.
3. Subjective refraction, using standard ETDRS methods, should be performed prior to measurement of BCVA and the appropriate correction worn in a trial frame.
4. The subject may be seated or may stand and the chart should be at eye level.
5. All eyes are first tested at 4 meters (m) including those that could not be refracted at 4m. Note: for eyes refracted at 1 meter, the additional +0.75 D sphere should be subtracted from the spherical correction before testing vision at 4m.
6. The right eye (OD) should be tested first using Chart 1 then the left eye (OS) is tested using Chart 2.
7. Each chart should remain hidden from view until the eye in question is to be examined.
8. If less than 20 letters are read with either eye at 4m the eye(s) with the reduced acuity is tested at 1m.

ETDRS Scoring

1. At the end of the test count up the number of letters read correctly by each eye.
2. If 1-meter testing was not required, then add 30 to get the ETDRS letters score.
3. If 1-meter testing was required, the ETDRS letters score is the sum of the letters read at 4 meters and at 1 meter.

To qualify for SF0166-C-001, the subject must have BCVA between 78 and 25 letters, inclusive, in the study eye at the screening/randomization visit using ETDRS testing. There is no visual acuity requirement for the non-study eye.

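### Randomization is stratified by baseline BCVA in the synopsis, but Section 9.7 does not carry the strata and no planned analysis of BCVA change uses them or baseline BCVA.

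*Combined protocol and SAP*

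**What the plan says.** - **Synopsis (Section 1.0), design:** "Randomization will be stratified by best-corrected visual acuity (BCVA) using Early Treatment Diabetic Retinopathy Study (ETDRS) testing", with the split "<40 letters versus ≥ 40 letters at Visit 1". The sentence does not say which eye sets the stratum.
- **Synopsis, inclusion criterion 3:** "BCVA between 78 and 25 letters, inclusive, in the study eye at the screening/randomization visit using ETDRS testing". Section 15.1 repeats this range.
- **Section 9.7:** "The randomization schedule will be blocked to ensure a balance of study arms at the study level". It gives neither a stratum nor a block size.
- **Sections 9.2 and 10.1, IWRS steps:** "the site will enter the required data into the IWRS in order to randomize the subject to a treatment arm" and "If subject is eligible, randomize the subject by entering information into the IWRS". Neither names BCVA as an entry.
- **Section 11.3.2:** the secondary outcome is mean change from baseline in BCVA. For its analysis, 11.3.2.2 says "Descriptive statistics will be used to summarize the study outcomes". No stratum, covariate or between-dose estimate appears there, in 11.3.1.2 for the OCT outcomes, or in the synopsis methods. Sections 11.3.1.1 and 11.3.2.1 plan no formal tests.
- **Synopsis, sample size:** 20 per arm is expected to be enough to tell the two dose groups apart on efficacy and safety.

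**The concern.** The design singles out baseline BCVA as the factor to balance, and the plan then makes no further use of it. Baseline BCVA is also the starting value of the secondary outcome and limits how many letters an eye can gain. With 20 per arm and no adjusted estimate, readers will compare raw mean changes, and part of any difference may reflect where the arms started. Randomization makes this noise rather than systematic bias, but the noise can be removed with data already collected.

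There is a smaller documentary gap. The section that describes the schedule leaves out a design feature stated in the synopsis, so the schedule cannot be built from Section 9.7 alone.

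**Working it through.** **1. The text.** The strata appear in the synopsis design paragraph and nowhere else in the current text. Sections 9.0, 9.2, 9.7 and 10.1 describe randomization without them. Section 11 and the synopsis methods use neither the strata nor baseline BCVA. The plan gives no stratum sizes, expected BCVA distribution or block size, so it has no figure of its own to reproduce on this point.

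**2. What the cut controls.** Eligible scores run from 25 to 78, which is 78 - 25 + 1 = 54 values. Of these, 15 (25 to 39) lie below the cut and 39 (40 to 78) at or above it. Stratified blocks balance the number of subjects on each side of 40. They do not balance scores within 40 to 78.

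**3. Size of the remaining imbalance.** The distribution has to be assumed. I used a uniform on 25-78, and normals with mean 50, 55, 60 or 65 and SD 10, 12 or 14, truncated to 25-78 (integer scores; 13 scenarios). With p the share below 40:

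- Share of variance between strata: R² = p(1 - p)(mean_high - mean_low)² / variance.
- SD of the arm difference in mean baseline BCVA, strata balanced: SD × √(1 - R²) × √(2/20). Without strata, omit the √(1 - R²) term.

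Uniform case: p = 15/54; stratum means 32 and 59; variance (54² - 1)/12 = 242.9. R² = (15 × 39/54²) × 27² / 242.9 = 146.25/242.9 = 0.60. SD with strata = √(242.9 × 0.398 × 0.1) = 3.1 letters; without strata, √(242.9 × 0.1) = 4.9.

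| Assumed distribution | Expected below 40, of 40 | R² at the 40 cut | SD without strata | SD with strata |
|---|---|---|---|---|
| Uniform 25-78 | 11.1 | 60% | 4.9 | 3.1 |
| Normal 50/10 | 5.7 | 41% | 3.1 | 2.4 |
| Normal 50/12 | 7.1 | 46% | 3.5 | 2.6 |
| Normal 55/12 | 3.8 | 35% | 3.5 | 2.8 |
| Normal 60/12 | 1.8 | 23% | 3.3 | 2.9 |
| Normal 65/10 | 0.2 | 6% | 2.7 | 2.6 |

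Over all 13 scenarios the SD with strata is 2.4 to 3.1 letters. It is 2.6 to 3.1 in every scenario except normal 50/10. The formula assumes an exactly even split within each stratum. Simulating blocks of 4 within strata (an assumed size) gives slightly more, about 2.5 to 3.3 letters. The range is narrow because distributions with a wide spread are also those in which the 40 cut removes more of it.

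**4. From baseline to change.** A baseline imbalance d moves the raw difference in mean change by b × d, where b is the slope of change on baseline. The documents give no slope. At assumed values of -0.1 and -0.4, and d = 3 letters, the shift has size 0.1 × 3 = 0.3 to 0.4 × 3 = 1.2 letters.

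**5. Price of adjusting.** One covariate costs one residual degree of freedom: 37 instead of 38 with 40 subjects, or 27 instead of 28 with the 30 completers that Section 8 allows for.

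**The case against.** The strongest reply is that nothing here is an error. Section 9.7 is silent, not contradictory: blocks formed within BCVA strata also keep the arms balanced at study level, and the phrase may only mean that blocking is not by site. The synopsis is working text in this protocol, since Section 8 sends the reader there for the full eligibility criteria. The data entered into the IWRS may well include BCVA. The trial plans no tests, so no p-value or interval is distorted by leaving the strata out, and stratified allocation improves balance whether or not the analysis adjusts.

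Most of this stands. A reader might infer that 9.7 overrides the synopsis and that the trial is in fact unstratified; the wording does not support that. The absence of testing does not remove the main point, however. An adjusted difference with an interval is estimation, and the synopsis itself expects the trial to separate the doses.

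A reader might also infer from the off-center cut that it balances little, that the lower stratum will be almost empty, or that the cut should move. The documents give no BCVA distribution. Across the assumed ones, the cut captures 6% to 60% of the baseline variance, with 0.2 to 11 of 40 subjects expected below it. A cut set to separate poor-vision eyes may be deliberate. Finally, a baseline imbalance does not pass in full into a change score; only the slope's share of it does.

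**Conclusion.** The point holds as an omission with a modest effect. The stratification factor is stated once, is not carried into Section 9.7, and is not used in Section 11, where its continuous form would sharpen the dose comparison on the secondary outcome. What needs no assumption is that the upper stratum spans 39 of 54 eligible scores and that imbalance within it is left to chance. The sizes do rest on assumptions: a between-arm SD of about 2.4 to 3.1 letters at baseline on the distributions listed, with 20 per arm, and a shift of 0.3 to 1.2 letters in the BCVA-change difference for a 3-letter imbalance at slopes of -0.1 to -0.4. No effect on the OCT outcomes has been quantified. The descriptive analysis is not invalid as it stands.

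**What to change.** 1. **Section 11.3.2.2.** Keep the descriptive summaries. Add the between-dose difference in mean BCVA change with a 95% CI, from a linear model with dose group and continuous study-eye Visit 1 BCVA, at each visit where the change is summarized. Label it as estimation, not a hypothesis test. The continuous score also covers the variation within 40 to 78 letters that the strata leave open, and it works whatever the stratum sizes turn out to be.
2. **Section 9.7.** For consistency, add one sentence stating that blocks are formed within the Section 1.0 BCVA strata, and that the stratum is set by the study eye if that is the intention.

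The cost is one model and one sentence. Visit 1 BCVA is already collected on both eyes, so no visit, measurement or subject is added. The stratum cut can stay where it is.
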